### 7.3.2 Erlotinib

Erlotinib 150 mg will be administered PO QD according to the prescribing information.  Treatment with erlotinib is continuous. Patients should take erlotinib as directed by the study investigator. Each dose should be taken with 8 oz (240 mL) of water on an empty stomach; i.e., at least 1 hour before or 2 hours after the ingestion of food.

If a patient misses a dose (i.e., does not take it within 6 hours of the scheduled time), he or she should resume taking erlotinib with their next scheduled dose. Missed or vomited doses will not be made up.

The investigator or designee will be responsible for distributing erlotinib to patients. A sufficient number of tablets will be provided to the patient to last until the next scheduled visit. Patients will be instructed to record daily doses taken or not taken on a patient diary, and will be instructed to bring their erlotinib tablets and diary to the next scheduled visit for reconciliation by site personnel.

# 7.4 Dose Modifications of Protocol-specified Treatment

### 7.4.1 CO-1686

No dose escalation above the starting dose is allowed. Two dose reduction steps are allowed for each patient. The dose reductions are from 500 mg BID (starting dose) to 375 mg BID, then to 250 mg BID. The dose of CO-1686 should not be reduced below 250 mg BID without prior sponsor approval.

For National Cancer Institute (NCI) Common Terminology Criteria for Adverse Events (CTCAE) Version 4.03 Grade 3 or 4 hematologic and non-hematologic toxicities (except for nausea/vomiting, alopecia, QTc prolongation and hyperglycemia), the dose should be initially reduced to 375 mg BID and, if persistent, to 250 mg BID for subsequent doses if the investigator and sponsor do not believe treatment discontinuation is required. Re-escalation of dose after resolution of AEs must be discussed and approved by sponsor prospectively.

Once the dose has been reduced, treatment continues at that dose level until the next visit; no dose escalation is possible between visits. If a patient continues to experience toxicity after 2-dose reductions, or if dosing with CO-1686 is interrupted for > 14 consecutive days due to toxicity, treatment should be discontinued unless otherwise agreed between the investigator and the sponsor before reintroduction of study drug.

## Management of Prolonged QTc

ECGs will be measured throughout the study as described in the protocol. Readings for QTc prolongation will be based on the average seen in the ECGs for each time point. Patients are required to have laboratory values for potassium and magnesium within normal limits at enrollment, and these electrolytes should be maintained within range during CO-1686 treatment, if necessary using supplementation. If QTC prolongation of CTCAE Grade 3 is observed, CO-1686 will be held until the event has improved to Grade 1. CO-1686 can then be re-started at a reduced dose upon approval by sponsor. After 2 dose reductions, if CTCAE Grade 3 or above QTc prolongation recurs, then CO-1686 will be discontinued unless agreed with the sponsor that additional dose reduction may be considered. If QTC prolongation changes of CTCAE Grade 4 are observed at any time, CO-1686 will be discontinued permanently.

# Management of Hyperglycemia

CO-1686 causes hyperglycemia in some patients secondary to inhibition of the insulin-like growth factor 1 receptor (IGF-1R) and insulin receptor (IR) kinases by a metabolite. Therefore, some patients will require addition of a glucose lowering medication and patients with pre-existing diabetes may require more frequent monitoring and/or adjustments of diabetic medication. Clinical experience with CO-1686 suggests hyperglycemia generally occurs within the first 3 weeks of treatment, leading to the need for more intensive glucose monitoring during the first several weeks of the study. In Phase 1/2 clinical trial experience, increased nausea, vomiting, decreased appetite, diarrhea, muscle cramps and fatigue have been reported in patients with hyperglycemia. Such patients must be closely monitored including assessment of fasting glucose levels and early initiation of anti-hyperglycemic therapy. As CO-1686-induced hyperglycemia is mediated through insulin resistance, agents that suppress glucose synthesis (metformin), increase sensitivity to insulin (glitazones) or increase glucose excretion (sodium- glucose cotransporter 2 [SGLT2] inhibitors) are expected to be more effective than those that increase plasma insulin (sulphonylureas or exogenous insulin). Metformin has been used most frequently in CO-1686 clinical studies and is, therefore, recommended as the initial agent to manage hyperglycemia in patients with normal renal function. In addition, preliminary data from the ongoing Study CO-1686-008 suggest that starting metformin at the same time CO-1686 therapy is initiated may prevent development of CO-1686-induced hyperglycemia. For all patients, irrespective of whether they are receiving metformin prophylactically or therapeutically, glucose monitoring should be conducted according to the following schedule:

Fasting glucose will be measured at the following visits: screening, C1D1, C1D4 (± 1 day), C1D8 (± 1 day), C1D15 (± 1 day), C2D1, C2D15 (± 1 day), C3D1, C4D1, C5D1, CND1 and End-of-Treatment Visit.

The following guidelines for management of hyperglycemia are based on experience in the Phase 1 study. Whilst the blood glucose thresholds for intervention outlined below should be followed, management of individual patients should be based on local practices and the treating physician's

judgment. In all cases, the prescribing information should be followed and maximum approved dose of anti-hyperglycemic agent should not be exceeded.

- 1. Additional monitoring outside of per protocol schedule (Table 9-1) is not needed if fasting glucose is less than 125 mg/dL (< 6.94 mmol/L).
- 2. If fasting glucose ≥ 125 mg/dL (≥ 6.94 mmol/L) and ≤ 160 mg/dL (≤ 8.88 mmol/L), patients will be asked to perform self-monitoring of blood glucose using finger stick blood testing (preferred choice) or urine dipstick testing (a urine dipstick can show a false-positive glucosuria in patients taking SGLT2 inhibitors). Initiation of anti-hyperglycemic therapy with metformin or anti-hyperglycemic agent of choice should be considered at this time, particularly for patients with symptoms of increased nausea, vomiting, decreased appetite, diarrhea, muscle cramps and fatigue. Tests should be performed at home QD for at least 2 weeks, taking note of time, fasted/fed state, and glucose levels in a monitoring log provided. Patients should bring this monitoring log to scheduled visits and review with treating physician. If patient observes at home 2 or more fasting blood glucose measurements > 160 mg/dL (> 8.88 mmol/L), and/or 2 or more random blood glucose measurements > 200 mg/dL (> 11.01 mmol/L) (or a combination of the 2), or 2 or more positive urine glucose testing before their next scheduled clinic visit, they should call their health care practitioner (HCP), inform the study site, and schedule a visit as soon as possible with the treating physician. Treatment with metformin or anti-hyperglycemic agent of choice should be started (See Figure 7-1).
- 3. If fasting blood glucose > 160 mg/dL (≥ 8.88 mmol/L) and < 250 mg/dL (≤ 13.87 mmol/L) on more than 2 occasions, start metformin or anti-hyperglycemic agent of choice. Patients should perform self-monitoring of blood glucose using finger stick blood testing or urine dipstick testing. Finger stick tests should be performed at home QD for at least 2 weeks, making note of time, fasted/fed state and glucose levels in a monitoring log provided. Patients should bring this monitoring log to scheduled visits and review with treating physician.
- 4. If fasting glucose ≥ 250 mg/dL (> 13.87 mmol/L), and the patient is not symptomatic, manage as for Step 3 above. If the patient is symptomatic, then hold CO-1686 and bring glucose under control acutely, if necessary using insulin with conversion to metformin or anti-hyperglycemic agent of choice once plasma glucose is controlled. Once patient is asymptomatic and deemed appropriate for additional therapy, CO-1686 may be re-introduced at a reduced dose, with concomitant metformin/anti-hyperglycemic agent of choice. Patients should perform self-monitoring of blood glucose using finger stick blood testing or urine dipstick testing. Finger stick tests should be performed at home BID for at least 2 weeks, before breakfast and before dinner, taking note of time, fasted/fed state and glucose levels in a monitoring log provided. Patients should bring this monitoring log to scheduled visits and review with treating physician.

[figure not shown]
Metformin is contraindicated in patients with renal disease or renal dysfunction, among others, and use should follow the package insert and approved label. In order to minimize known gastrointestinal (GI) toxicity associated with metformin use, the extended release form and taking medication at bedtime are recommended to improve tolerability. Additional recommendations to avoid GI toxicity with metformin include starting treatment at a reduced dose (500 mg QD) for 72 hours, increasing to 500 mg BID for 72 hours, and if necessary, and increasing up to 1,000 mg BID. If plasma glucose is not

adequately controlled with the regimen outlined above, then consider adding pioglitazone or a SGLT-2 inhibitor and consider consultation with an endocrinologist.

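### Section 7.4.1 hyperglycemia rule: 200 mg/dL is misprinted as 11.01 mmol/L, one 8.88 sign is wrong, and Step 3 has a stricter and less complete start rule than Step 2

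*Combined protocol and SAP*

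**What the plan says.** Section 7.4.1, Management of Hyperglycemia, gives numbered steps by fasting glucose, with each threshold in mg/dL and mmol/L.

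- **Step 2** covers 125 to 160 mg/dL inclusive; its upper end is printed as "≤ 160 mg/dL (≤ 8.88 mmol/L". The patient tests at home daily for at least two weeks, and about treatment the step says "Initiation of anti-hyperglycemic therapy with metformin or anti-hyperglycemic agent of choice should be considered at this time". The escalation rule begins "If patient observes at home 2 or more fasting blood glucose measurements" and sets the level at "> 160 mg/dL (> 8.88 mmol/L". Two or more random readings "> 200 mg/dL (> 11.01 mmol/L", a mix of the two kinds, or two or more positive urine tests also count. The patient then calls, is seen as soon as possible, and treatment should be started; the text points to Figure 7-1.
- **Step 3** covers the next band, with lower end "> 160 mg/dL (≥ 8.88 mmol/L" and upper end "< 250 mg/dL (≤ 13.87 mmol/L". Its trigger is "on more than 2 occasions, start metformin or anti-hyperglycemic agent of choice". The home-testing instruction comes after that condition.
- **Step 4** covers 250 mg/dL and above.

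The introduction to the steps says the thresholds should be followed but leaves the management of individual patients to local practice and the physician's judgment. Appendix D, Study Design, keeps the Section 7.4 hyperglycemia guidance in force in the extension and requires deviations to be agreed with the sponsor beforehand.

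**The concern.** The unit pairs should describe the same threshold, because sites work in one unit or the other. If they differ, the rule depends on the site's laboratory.

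The counts raise a different question. Two home fasting readings above 160 mg/dL are enough to start treatment in a patient who entered at 125 to 160. A patient first seen above 160 needs at least three under Step 3's wording, so the higher entry value has the stricter rule. There is also a gap. A single value of 125 to 160 leads to home testing and consideration of treatment, whereas a first or second clinic value of 161 to 249 is above Step 2's range and does not yet meet Step 3's count, so neither step addresses it.

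Hyperglycemia is a frequent effect of this drug. At 500 mg BID, the starting dose here, Table 3-2 shows it as treatment-related in 11 of 18 patients in Study CO-1686-008, and Table 3-1 shows it as a treatment-related serious event in 4 of 18. At stake is the timing of treatment for individual patients. Sample size, error rates and efficacy comparisons are not involved.

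**Working it through.** **Unit conversion.** The documents state no conversion factor, so it is taken from the section's own pairs.

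- 125 / 6.94 = 18.012
- 160 / 8.88 = 18.018
- 250 / 13.87 = 18.024

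The three agree closely. As a cross-check, multiplying mg/dL by 0.0555 (an assumed rounded factor) gives 6.94 for 125, 8.88 for 160 and 13.875 for 250 (printed 13.87), so the other pairs reproduce.

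For 200 mg/dL:

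- 200 / 18.012 = 11.104
- 200 / 18.018 = 11.100
- 200 / 18.024 = 11.096

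All round to 11.10. Dividing by 18 exactly gives 11.11. No variant gives 11.01, which looks like transposed digits. Converting back, 11.01 × 18.018 = 198.4 mg/dL, which is 200 − 198.4 = 1.6 mg/dL too low.

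**The 160 mg/dL sign.** 8.88 × 18.012 = 159.9 and 8.88 × 18.024 = 160.1, so 8.88 is the right number. Step 2 includes 8.88 at its upper end and uses a strict sign for the home trigger. Step 3 uses a strict sign in mg/dL but a non-strict one in mmol/L. A result of exactly 8.88 mmol/L therefore belongs to both steps, while 160 mg/dL belongs to Step 2 only.

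**The 250 mg/dL boundary.** The signs differ between units here too, but the result is consistent: 250 / 18.012 = 13.880 and 250 / 18.018 = 13.875, both above 13.87. A value of 250 mg/dL goes to Step 4 in either unit, and no change is needed.

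**The count.** More than two means at least three. The quantity of interest is the time from the reading that would satisfy a two-reading rule to the one that satisfies Step 3.

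- *Home and clinic readings both count.* Take a clinic value above 160 on day 0 and home fasting values above 160 on days 1 and 2. Two home readings are reached on day 2 (Step 2), and three readings in all are also reached on day 2 (Step 3). Difference: 0 days.
- *Only home readings count, one per day.* Two are reached on day 2 and three on day 3. Difference: 1 day.
- *Only scheduled clinic readings count, all stay in the band, and the physician waits.* Nominal days, with Cycle 2 Day 1 falling 28 days after Cycle 1 Day 1, are C1D4 = 4, C1D8 = 8, C1D15 = 15, C2D1 = 29 and C2D15 = 43. First high value on Day 4: 15 − 8 = 7 days. On Day 8: 29 − 15 = 14 days. On Day 15: 43 − 29 = 14 days. Visit windows are ignored.
- *The same reading in the extension.* Appendix D Table 4 schedules chemistry on Day 1 of each cycle, and Appendix D gives 28-day cycles, so consecutive clinic readings are about 28 days apart.

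The first two cases assume that home testing is already under way. Step 3 taken literally does not order it before the count is met.

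**The case against.** The strongest reply is that the two steps serve different pathways. Step 2 tells a patient at home when to call; Step 3 tells a physician what to do with someone already above 160 mg/dL. The threshold is the same in both, and Step 3 does not forbid starting sooner. Around it, Section 7.4.1 calls for early treatment in hyperglycemic patients with the listed symptoms, mentions metformin given from the start of CO-1686, and builds in clinical judgment. Figure 7-1, to which Step 2 refers, is not visible in this copy and may state one count. Its footnote confines the guidance to patients non-diabetic at study start.

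Much of this stands. A reader might infer that patients with higher glucose must wait weeks for treatment, or that a physician who starts after two readings has deviated from the protocol. The documents support neither inference: the long delays need several assumptions together, and judgment is part of the guidance. A reader might also infer that 11.01 exposes patients to harm; it does not, because it triggers slightly early and is one of several alternative triggers.

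What does not stand is that the text is therefore consistent. Judgment softens the difference in counts without reconciling it. A figure with a single count would still disagree with one of the two steps. Nothing nearby corrects 11.01 or the 8.88 sign.

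**Conclusion.** Two items are wrong as written: 11.01 mmol/L should be 11.10, an error of about 1.6 mg/dL in the cautious direction, and Step 3's sign at 8.88 mmol/L should be strict, which affects one boundary value. The third is an inconsistency between steps, together with a missing instruction at the first or second reading of 161 to 249 mg/dL. How much the third matters depends on which readings count, which Step 3 does not say, and it is subject to what Figure 7-1 shows.

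The practical reach is small. Appendix D closes enrolment and removes crossover, and Section 7.4.1 says onset is generally within the first three weeks of treatment, so few remaining patients should newly meet the rule; the documents give no number. The 7-to-14-day figures rest on early-cycle visits that the extension schedule has replaced. It is still worth correcting, because the guidance remains in force and the repair is easy.

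**What to change.** In Section 7.4.1:

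1. Step 2: change 11.01 to 11.10 mmol/L.
2. Step 3: make the lower bound strictly greater than 8.88 mmol/L.
3. Step 3: begin home monitoring at the first fasting value above 160 mg/dL, and start treatment at two or more such readings, home or clinic.

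Before making the third change, check Figure 7-1 and make text and figure agree. If the clinical team intended three clinic readings in Step 3, that should be stated instead, with an instruction for the first two. The cost is one number, one sign, a sentence or so of text and a check of the figure. No analysis changes.

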## 8.1.3 CYP450 Isozyme Inhibitors and Inducers

*In vitro* studies suggested the potential involvement of CYP2C8 in CO-1686 metabolism and thus, clinically, there is potential for CO-1686 plasma concentrations to be increased in the presence of co-administered potent inhibitors of CYP2C8. CYP2D6 appears to play a minor role, but its involvement in CO-1686 metabolism cannot be fully ruled out. Therefore, caution should be exercised with strong inhibitors of CYP2C8 and CYP2D6. For example, CYP2C8 inhibitors such as gemfibrozil, trimethoprim, glitazones, montelukast, and quercetin and CYP2D6 inhibitors such as bupropion, fluoxetine, paroxetine, and quinidine should be avoided.

Inducers of CYP2C8 and CYP2D6 have the potential to decrease CO-1686 exposure. Therefore, caution should be exercised with rifampin, an inducer of CYP2C8. No inducers of CYP2D6 have been identified.

Regarding strong inhibitors or inducers of CYP2C8 and CYP2D6, selection of an alternative concomitant medication with no or minimal enzyme inhibition or induction potential is recommended.

Caution should be exercised in patients receiving CO-1686 and requiring concomitant medication with warfarin (Coumadin®; patients known to require concomitant therapy with anticoagulant therapy such as warfarin should have international normalized ratio (INR) monitored at screening and during the study), NSAIDs, or clopidogrel, as CO-1686 moderately inhibited CYP2C8, CYP2C9, and CYP2C19 activities *in vitro*.

A list of inhibitors and inducers of CYP2C8 and CYP2D6 to be avoided or used with caution in patients receiving CO-1686 is attached in Appendix C.

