# Appendix C

# Inhibitors and Inducers of CYP2C8, CYP2D6 and P-gp

The following list of inhibitors and inducers of CYP2C8, CYP2D6 and P-gp are to be avoided or used with caution in patients receiving CO-1686. Selection of an alternative concomitant medication with no or minimal enzyme inhibition or induction potential is recommended.

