## Inhibitors and Inducers of CYP2C8 and CYP2D6

CYP Enzyme	Inhibitors	Inducers
	(Avoid)	(Caution)
CYP2C8	gemfibrozil trimethoprim glitazones montelukast quercetin	rifampin
CYP2D6	bupropion fluoxetine paroxetine quinidine	

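### Section 7.4.1 suggests pioglitazone for uncontrolled hyperglycemia, while Section 8.1.3 and Appendix C say to avoid glitazones with CO-1686

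*Combined protocol and SAP*

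**What the plan says.** Section 7.4.1 (Management of Hyperglycemia) attributes the hyperglycemia to insulin resistance. It expects three kinds of agent to work better than sulphonylureas or insulin: metformin, drugs that "increase sensitivity to insulin (glitazones) or increase glucose excretion", the last group being the SGLT2 inhibitors. Metformin is the recommended first agent when renal function is normal. Step 3 tells sites to "start metformin or anti-hyperglycemic agent of choice", and steps 2 and 4 leave the same free choice of agent. If the metformin regimen is not enough, the instruction is "then consider adding pioglitazone or a SGLT-2 inhibitor and consider consultation with an endocrinologist".

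Section 8.1.3 covers drugs that may interact with CO-1686. Its reason for concern is that "there is potential for CO-1686 plasma concentrations to be increased in the presence of co-administered potent inhibitors of CYP2C8". It then states: "CYP2C8 inhibitors such as gemfibrozil, trimethoprim, glitazones, montelukast, and quercetin and CYP2D6 inhibitors such as bupropion, fluoxetine, paroxetine, and quinidine should be avoided".

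Appendix C repeats the list. Its CYP2C8 inhibitor entry reads "gemfibrozil trimethoprim glitazones montelukast quercetin", in a column headed Avoid.

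Appendix D keeps the Section 7.4 hyperglycemia guidance in force for the Extension Phase and asks for prior sponsor agreement to any departure from it.

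**The concern.** Two parts of the same protocol give opposite advice about one drug class in the same patients. A treating physician managing high glucose will turn to Section 7.4.1, because that is where the glucose thresholds and treatment steps are. Nothing in its readable text shows that one of the two suggested add-ons is on the protocol's own avoid list.

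The sponsor check in Appendix D would not catch this. It applies to departures from the Section 7.4 guidance, and pioglitazone is within that guidance.

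What is at stake is patient safety, through the mechanism the protocol itself names: a possible rise in CO-1686 concentration. No further harm is claimed, and the statistical design is not involved.

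**Working it through.** No alpha, power, event count or sample size enters this point, and the plan gives no figure to reproduce. The check compares the texts.

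| Place | What it says about glitazones |
|---|---|
| 7.4.1, introductory paragraph | One of three classes expected to be more effective |
| 7.4.1, steps 2 to 4 | Free choice of agent; glitazones not excluded |
| 7.4.1, closing sentence on metformin | Pioglitazone named as one of two add-ons |
| 8.1.3 | Named among CYP2C8 inhibitors to avoid |
| Appendix C, CYP table | In the inhibitor column headed Avoid |
| Appendix D | Section 7.4 guidance still applies |

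**Step 1. Is there a direct conflict?** Yes, in one sentence. Section 7.4.1 proposes pioglitazone; Section 8.1.3 and Appendix C say to avoid its class. The other two 7.4.1 entries do not contradict Section 8.1.3 by themselves. The class statement is about expected effect, and the free choice of agent can be read together with Section 8.1.3. They matter because neither alerts the reader.

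**Step 2. Does an exception reconcile the texts?** None was found in the readable text of 7.4.1, 8.1.3, 8.1.5 or Appendix C. Section 7.4.1 does tell sites to follow prescribing information and not exceed the maximum approved dose. That is general and mentions neither CYP2C8 nor CO-1686 exposure.

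**Step 3. Does the softer wording reconcile them?** Appendix C introduces its lists as agents that "are to be avoided or used with caution in patients receiving CO-1686". The tables then separate the two categories. CYP2C8 and CYP2D6 inhibitors are under Avoid; CYP inducers and all P-gp agents are under Caution. Glitazones are under Avoid.

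**Step 4. How much of the guidance is affected?**
- Add-ons named: pioglitazone and an SGLT-2 inhibitor. On the avoid list: 1 of 2.
- Classes called more effective: metformin, glitazones, SGLT2 inhibitors. On the avoid list: 1 of 3.
- Section 7.4.1 says metformin is contraindicated in renal disease or dysfunction. For those patients 3 − 1 = 2 of the favored classes remain, and 1 of those 2 is on the avoid list.

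These are counts of options, not of patients. Metformin and SGLT-2 inhibitors appear on no list in Sections 8.1.3, 8.1.4 or Appendix C, so a compliant route exists.

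**Step 5. How does the protocol treat comparable cases?** Section 8.1 requires extra ECGs and a monitoring plan agreed with the sponsor when a QT-prolonging drug is needed. Section 8.1.3 attaches INR monitoring to warfarin, and Section 8.1.4 attaches drug-level monitoring to digoxin. Pioglitazone is suggested with no such safeguard, which looks more like an oversight than a recorded benefit-risk decision.

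**The case against.** The best counter-argument is that neither side of the clash is absolute. Section 8.1.3 bases its concern on potent inhibitors and on in vitro findings, asks for caution with strong ones, and offers the avoid list as examples. It ends by saying that, for strong inhibitors or inducers, an alternative "concomitant medication with no or minimal enzyme inhibition or induction potential is recommended". The documents never call pioglitazone a strong inhibitor. Section 8.1.5 lets investigators give treatment they consider necessary. Section 7.4.1 only asks sites to consider pioglitazone, offers an SGLT-2 inhibitor beside it, suggests an endocrinologist, and defers to local practice and clinical judgment.

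That correctly describes the tone and means pioglitazone is not strictly prohibited. It does not remove the conflict. Judgment requires knowing about the interaction, and Section 7.4.1 does not mention it.

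The second argument is reach. Appendix D closes enrollment and removes crossover to CO-1686, and Section 7.4.1 says hyperglycemia generally appears in the first three weeks of treatment. Few continuing patients are likely to reach the add-on step for the first time. Those who continue have chemistry, adverse events and concomitant medications reviewed each cycle. This stands and limits the practical weight of the point, but the instruction remains in force for anyone still on CO-1686.

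Third, the Figure 7-1 algorithm is not reproduced in the text available here, so a note inside it cannot be ruled out. Its visible footnotes contain no such warning.

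**Conclusion.** The concern holds. Section 7.4.1 suggests a drug from a class that Section 8.1.3 and Appendix C say to avoid with CO-1686, and no readable text reconciles them. The direct clash is confined to one sentence and affects one of its two named options.

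The number of patients exposed and the size of any change in CO-1686 concentration are not given in the documents, and the conclusion depends on neither. It assumes that Figure 7-1 contains no overriding note. The documents cannot show which instruction is pharmacologically right, only that both should not stand unreconciled. The point should be fixed on safety and consistency grounds; the efficacy analysis is unaffected.

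**What to change.** In the second-line sentence of Section 7.4.1, delete pioglitazone and add a pointer, for example: *If glucose remains uncontrolled, consider an SGLT-2 inhibitor and referral to an endocrinologist. Avoid glitazones with CO-1686; see Section 8.1.3 and Appendix C.* Put the same cross-reference where the section names glitazones as a class and where steps 2 to 4 allow a free choice of agent. Check Figure 7-1 for matching wording. Because step 2 warns that SGLT2 inhibitors can give false-positive urine glucose, remind sites to use finger-stick monitoring for those patients.

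If the sponsor's pharmacology team concludes that glitazones are acceptable with CO-1686, make the opposite change: remove them from the avoid lists in Section 8.1.3 and Appendix C.

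Either way the change is wording only, by clarification letter or amendment, with no new data, procedures or visits. If made as an amendment, it needs the ethics committee approval and regulatory submission described in Section 13.7.

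### Section 7.4.1 offers pioglitazone for CO-1686 hyperglycemia, while Section 8.1.3 and Appendix C say to avoid glitazones with CO-1686

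*Combined protocol and SAP*

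**What the plan says.** Section 7.4.1 (Management of Hyperglycemia) explains that CO-1686 hyperglycemia works through insulin resistance. Three classes are therefore expected to do better than sulphonylureas or insulin: metformin, drugs that "increase sensitivity to insulin (glitazones"), and SGLT2 inhibitors. Metformin is the recommended first agent in patients with normal renal function. Step 3 says to "start metformin or anti-hyperglycemic agent of choice". Step 4 covers symptomatic patients whose drug was held: "CO-1686 may be re-introduced at a reduced dose, with concomitant metformin/anti-hyperglycemic agent of choice". If the metformin regimen is not enough, the site should "then consider adding pioglitazone or a SGLT-2 inhibitor and consider consultation with an endocrinologist".

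Section 8.1.3 says that potent CYP2C8 inhibitors could raise CO-1686 concentrations, and then: "CYP2C8 inhibitors such as gemfibrozil, trimethoprim, glitazones, montelukast, and quercetin and CYP2D6 inhibitors such as bupropion, fluoxetine, paroxetine, and quinidine should be avoided". For strong inhibitors or inducers it adds that "selection of an alternative concomitant medication with no or minimal enzyme inhibition or induction potential is recommended".

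Appendix C introduces its lists as drugs that "are to be avoided or used with caution in patients receiving CO-1686". In its table, the CYP2C8 inhibitor cell reads "gemfibrozil trimethoprim glitazones montelukast quercetin" and stands in the column headed Avoid. The Caution heading is used for the inducers and for the P-gp lists.

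Appendix D (Treatment Regimen and Duration of Therapy) requires the Section 7.4 hyperglycemia and QTc guidance to be followed in the Extension Phase. Modifications or deviations from that guidance must be agreed with the sponsor first.

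**The concern.** A site that follows Section 7.4.1 as written can start a drug that Section 8.1.3 tells it to avoid, in a patient who already has a CO-1686 toxicity. A physician reading only 7.4.1 is not told that an interaction is suspected, because that section refers to neither 8.1.3 nor Appendix C. Adding pioglitazone complies with Section 7.4, so the Extension Phase rule on sponsor discussion of deviations would not catch it either.

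At stake is an unplanned rise in CO-1686 exposure, with no check linked to starting the glitazone. Section 8.1 shows that the protocol can handle this kind of situation: a drug that may prolong QT needs an ECG monitoring plan agreed with the sponsor before it is started. Glitazones have no equivalent step.

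**Working it through.** The plan states no figure to reproduce. The check is whether any text reconciles the two instructions, and what the documents allow one to say about consequences.

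**1. Every mention of the class**

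| Place | Instruction on glitazones |
|---|---|
| 7.4.1, choice of agents | One of three classes expected to be more effective |
| 7.4.1, inadequate control | Consider pioglitazone or an SGLT-2 inhibitor |
| 8.1.3 | Named among CYP2C8 inhibitors to avoid |
| Appendix C table | Listed under Avoid |

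Two places support use and two say avoid.

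**2. Text that might reconcile them**

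- Section 7.4.1 defers to local practice, physician judgment and the prescribing information. It does not mention CYP2C8.
- Section 8.1.5 gives the investigator general discretion over necessary therapies, with no glitazone exception.
- Section 8.1.3 speaks of caution for strong inhibitors, and the Appendix C introduction allows caution for the list as a whole. Both places then put glitazones by name under avoid.
- Figure 7-1, to which step 2 of 7.4.1 refers, is not shown. Its footnotes are available and do not mention the interaction.

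No available text reconciles the two.

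**3. What the documents show about QTc**

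- Exposure rose in proportion to dose from 500 to 1000 mg BID (Section 3.2.3).
- Treatment-related QT prolongation on HBr tablets (Table 3-2) was 0/18 at 500 mg BID, 2/17 (11.8%) at 625, 5/50 (10.0%) at 750 and 3/6 (50.0%) at 1000. The numbers are small and the top dose drives the pattern. At this study's dose the count is zero.
- In healthy volunteers at 500 mg BID, 3 of 6 had an asymptomatic QTc increase (Section 3.2.1, Study CO-1686-016). Its size is not given.
- Section 7.4.1 attributes hyperglycemia to a metabolite. Appendix D says that NAT2 acts on metabolites M502 and M460, and that acetylator status relates most clearly to hyperglycemia and QT prolongation. Nothing says what CYP2C8 inhibition does to those metabolites.

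The protocol's reason to avoid glitazones is therefore a possible rise in parent-drug concentration. Neither the direction nor the size of any effect on QTc or glucose can be derived from the documents.

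**4. Whether a count of affected patients can be built**

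The nearest figure is in Appendix D, Table 2: two or more glucose values above 250 mg/dL in (51 + 36 + 7)/635 = 94/635 = 14.8%. This pools 500 to 1000 mg BID, does not show that metformin had failed, and comes with no data on glitazone use. Any count would need an uptake rate that the documents do not supply, so none is given.

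**5. Monitoring already in place**

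Table 9-1 schedules triplicate ECGs at C1D1, C1D8, C1D15 and each later cycle visit. Section 7.4.1 sets hold, reduce and stop rules for QTc whatever the cause. In the Extension Phase, after Cycle 12, patients whose QT has stayed below 470 ms may have ECGs every third cycle, which is 3 × 28 = 84 days apart. Hyperglycemia generally appears in the first 3 weeks, when ECGs are closer together.

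**The case against.** The strongest reply is that 7.4.1 is permissive: metformin comes first, pioglitazone is only to be considered, an SGLT-2 inhibitor stands beside it, and endocrinology advice is suggested. Section 8.1.3 rests on in vitro data and speaks of potent or strong inhibitors, and the documents never call glitazones strong. Scheduled ECGs and the QTc rules apply in any case. With enrolment closed and onset mostly early, few new glitazone decisions remain. All of this stands and limits the weight of the point. It does not remove the contradiction, because 8.1.3 and the Appendix C table name the class under avoid.

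A reader might infer more than the documents support in four ways:

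- **Glitazone use would worsen QTc.** The healthy-volunteer result invites this, but the patient data at the same dose show 0/18, and the metabolite link leaves the effect of CYP2C8 inhibition open.
- **The step 4 restart is the dangerous case.** That restart is at a reduced dose, which works against any rise in exposure.
- **Diabetic patients already on a glitazone fall into the conflict.** Figure 7-1's footnote limits the guidelines to patients who were non-diabetic at study start. For others, 8.1.3 is the instruction that applies.
- **A share of patients affected can be quoted.** That would rest on an assumed uptake.

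One limit runs the other way: Figure 7-1 might contain a reconciling note, and this could not be checked.

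**Conclusion.** Section 7.4.1 and Section 8.1.3 with Appendix C give opposite instructions on glitazones with CO-1686, and no available text resolves them. The conclusion rests on the wording alone and assumes that Figure 7-1 carries no exception. The documents do not show which section is right, only that both cannot be followed when pioglitazone is chosen.

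This is a minor safety-consistency correction. The size of the interaction, its effect on QTc or hyperglycemia, and the extent of glitazone use are all unknown. Few patients are likely to be affected now, although the number still on treatment is not stated. The primary PFS analysis is untouched.

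**What to change.** In Section 7.4.1:

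- remove glitazones from the favoured classes;
- name only an SGLT-2 inhibitor as the add-on;
- word the free choice as an anti-hyperglycemic agent other than a glitazone, with a reference to 8.1.3;
- align Figure 7-1 if it shows pioglitazone.

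This follows 8.1.3's own preference for alternatives with little or no enzyme inhibition. Where no alternative is suitable, for example in a patient who cannot take metformin, allow a glitazone only with prior sponsor agreement and an ECG check, on the model of Section 8.1 for QT-prolonging drugs.

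If the sponsor holds data showing no relevant interaction, it should instead write a glitazone exception into 8.1.3 and Appendix C and refer to it from 7.4.1.

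The cost is a text edit, which Appendix D would carry to patients still on treatment, and an occasional sponsor contact and ECG. The downside of the first route is one fewer readily available class. That matters most in renal dysfunction, where metformin is contraindicated, since entry allowed creatinine up to 1.5 × ULN. The second route keeps the class available.
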